### Chronic Pain

The effect of genotype-guided opioid therapy on secondary endpoints pain intensity reduction and opioid misuse score will be assessed by comparing the Intervention group subset with CYP2D6 IM or PM phenotypes to the Control group subset with CYP2D6 IM or PM phenotypes using a two-sided two-sample t-test or Mann Whitney test, as appropriate, with a type 1 error of 0.05. The effect of genotype guided opioid therapy on the secondary endpoint clinically significant pain reduction, defined as a 30% decrease, will be assessed by comparing the Intervention group subset with CYP2D6 IM or PM phenotypes the Control group subset with CYP2D6 IM or PM phenotypes using a test of two-proportions with an alpha of 0.05. Participants that have other CYP2D6 phenotypes will not be included in these analyses.

### Depression

The effect of genotype guided antidepressants therapy on the secondary endpoint depression remission and achieving 5% reduction in PHQ-8 scores will be assessed by comparing the Intervention group subset with CYP2D6 UM or PM or CYP2C19 UM, RM, or PM phenotypes the

Control group subset with CYP2D6 UM or PM or CYP2C19UM, RM, or PM phenotypes using a test of two-proportions with an alpha of 0.05. The effect of genotype guided antidepressants therapy on the secondary endpoints, medication adherence, PHQ-8 scores, and medication side effect severity burden, will be assessed by comparing the Intervention group subset with CYP2D6 UM or PM or CYP2C19 UM, RM, or PM phenotypes the Control group subset with CYP2D6 UM or PM or CYP2C19 UM, RM, or PM phenotypes using a two-sided Mann Whitney test with an alpha of 0.05. Participants that do not have metabolizer phenotypes will not be included in these analyses.

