Safety Assessment and Monitoring-Events of Interest Section 8.2	
Redefined the text to:
 
 
“Participant reported emergency department visits and hospitalizations will be collected in the 1, 3, and 6-month follow-up participant surveys. EHR will be used as an additional source for emergency department visits and hospitalizations, up to approximately 12 after the last patient is randomized. For the details of collecting EHR data, see Protocol section 7.8 and MOP. EHR results will be sent to the CC via secure data transfer and formatted for data analyses.”
 
	7/2/2021
Statistical Analysis Plan and Sample Size: Analysis of Secondary Endpoints Section 10.5	
Depression:
 
 
Added text “and achieving 5% reduction in PHQ-8 scores “and “PHQ-8 scores”
 
	7/2/2021

Data Management: Data Entry and Record Keeping Section 11.1	
 
Removed text: “automatically “ and “To verify the accuracy of automatic import of results into the participant’s records, laboratories will also transfer raw data in whatever format produced locally to the CC via secure file transfer after the first patient sample has been processed and at other intervals as described in the MOP.”
 
Added text: “The accuracy of the import of laboratory results will be verified by comparing the results recorded in the study database to an external record of the result for a subset of the study participants. See MOP for details.”
 
	7/2/2021
Data Management: Data Element Definitions Section 11.2	
Depression Remission:
 
 
Added text: B. Whether or not the PHQ-8 scores are <math>\leq 4</math>, which is equivalent to depression severity being none-mild.”
 
Added term definition: “Depression (PHQ-8) score: The sum of the responses to the PHQ-8 survey, range from 0 to 24.”
 
Removed text in Opioid Usage: “and post discharge inpatient opioid usage immediate post-surgery collected from EHR queries”
 
	7/2/2021
References	Removed reference for QIDS depression scale and added in reference for PHQ-8 depression scale.	7/2/2021

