##### Chronic pain

[figure not shown]
1. Pain reduction magnitude at 3-month post return of genetic testing results to provider, relative to baseline
2. Proportion of participants achieving clinically significant pain reduction (30% reduction from baseline) at 3-months post return of genetic testing results to provider
3. Prescription pain medication misuse at 3-months post return of genetic testing results to provider

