##### Depression

1. Change in PHQ-8 score between baseline and 3 months
2. Achieve 50% reduction in PHQ-8 scores at 3 months, relative to baseline
3. Medication side effects severity burden at 3 months
4. Participant medication adherence at 3 months
5. Achieve remission at 6 months, defined as PROMIS depression score  $\leq 16$
6. Achieve remission at 6 months, defined as PHQ-8 score  $\leq 4$

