## 10.2 General Statistical Methods

A detailed statistical analysis plan will be developed for each trial (acute pain, chronic pain, and

depression) and contained in a separate document. Prior to analysis, each trial study population details, including the number randomized, in each treatment arm, and lost to follow-up will be described. Baseline participant characteristics will be summarized as means, standard deviations, medians, and 25th, 75th percentiles for continuous variables, and as counts and percentages for categorical variables. Model assumptions will be examined prior to analysis and transformations implemented, if necessary, to more adequately meet the assumptions. Unless otherwise stated, hypotheses will be tested as two-sided with a significance level of 0.05.

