### **10.9 Multiplicity**

With the primary and various secondary endpoints that have been outlined, there is a multiplicity of analyses to be performed, which leads to an increased probability that at least one of the comparisons could be "significant" by chance. Adjusting for the effects of the repeated significance testing for the

multiplicity of secondary endpoints would require that very small significance levels be used for every comparison. Therefore, rather than adjusting for multiple comparisons, we will be conservative in the interpretation of the analyses, considering the degree of significance, and looking for consistency across endpoints. The nominal (unadjusted) p-value for each comparison will be reported to aid in the overall interpretation. We have also prespecified the primary and secondary outcome variables to avoid over-interpretation of strictly exploratory comparisons.

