### 11.2 Data Element Definitions

Clinically significant pain reduction: Whether or not the pain reduction score is  $\leq 0.7$ . If the pain reduction score is  $\leq 0.7$ , clinically significant pain reduction is achieved, if pain reduction scores is  $> 0.7$ , clinically significant pain reduction is not achieved.

Depression symptom control: The change in the PROMIS Emotional Distress - Depression 8b or PROIMIS pediatric Depression 8a survey depression score from baseline to time t.

Depression remission: A. Whether or not the summed raw PROMIS emotional distress depression 8b survey responses are  $\leq 16$ , which is equivalent to the participant responding “rarely” or “never” to most or all of the PROMIS emotional distress - depression 8b survey questions. B. Whether or not the PHQ-8 scores are  $\leq 4$ , which is equivalent to depression severity being none-mild.

Depression (PHQ-8) score: The sum of the responses to the PHQ-8 survey, range from 0 to 24.

Depression (T) score: The T-score converted summed responses to the PROMIS emotional distress depression 8b survey. The T-score conversion is centered around 50 with standard deviation of 10.

Depression severity: The depression score converted to depression severity (none, mild, moderate, severe) based on the scoring guide for the PROMIS emotional distress depression 8b survey.

Medication adherence: The scored responses to the Voils Medication Adherence survey.

Medication concordance: Whether or not the medication the participant is prescribed after the intervention is concordant with the participants CYP2D6 and, for the depression trial, CYP2C19 phenotype.

Medication side effects severity burden: (Depression only) The sum of the scored severity (none = 0, mild = 1, moderate = 2, severe = 3) for common SSRI side effects.

Opioid misuse score: The T-score converted summed responses to the PROMIS prescription medication misuse 7a survey. The T-score conversion is centered around 50 with standard deviation of 10.

Opioid persistence: Defined as  $\geq 1$  opioid prescription refill between 90 days and 180 days after the surgical procedure.

Opioid usage: The average daily morphine equivalents in mg (MED) in past 7 days. MEDs will be calculated using data from the opioid usage survey.

Overall well-being: Defined as the T-score converted summed responses to the PROMIS 43/PROMIS 37 pediatrics survey. The T-score conversion is centered around 50 with standard deviation of 10.

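### Section 10.5 tests a 5% PHQ-8 reduction in the Depression trial, but the synopsis and section 3.2 define that secondary endpoint as a 50% reduction at 3 months from baseline

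*Combined protocol and SAP*

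**What the plan says.** The endpoint is defined twice in the same terms. The synopsis (Secondary Endpoints, Depression) and section 3.2 (Depression, item 2) both read "Achieve 50% reduction in PHQ-8 scores at 3 months, relative to baseline".

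Section 10.5 (Depression) gives the analysis: "depression remission and achieving 5% reduction in PHQ-8 scores will be assessed by comparing the Intervention group subset" with actionable phenotypes to the matching control subset, using a test of two proportions at alpha 0.05. The PHQ-8 part of that sentence has neither a visit nor a reference to baseline.

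Three other places bear on the point:

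- Section 11.2 defines the score ("Depression (PHQ-8) score: The sum of the responses to the PHQ-8 survey, range from 0 to 24") and defines PHQ-8 remission as a score of 4 or less. It has no entry for PHQ-8 response.
- The synopsis (Statistical Analyses, Depression) says that all depression secondary endpoints will be compared by a t-test, a Mann Whitney test or a test of two proportions, whichever suits. It sets no threshold and does not match tests to endpoints.
- Section 10.2 defers detail to other documents: "A detailed statistical analysis plan will be developed for each trial".

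**The concern.** One endpoint carries two thresholds that differ tenfold, and the smaller stands in the section an analyst would program from. Followed literally, section 10.5 would count almost any recorded fall in PHQ-8 as a response. That is a different outcome from the halving of the score that the endpoint sections promise.

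The missing time point adds to the ambiguity. Section 7.3 and Table 8 schedule the PHQ-8 at baseline, 3 months and 6 months, so section 10.5 alone does not say which follow-up visit counts.

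At stake is what this secondary result would mean. Section 10.9 makes no multiplicity adjustment for secondary endpoints and states "The nominal (unadjusted) p-value for each comparison will be reported to aid in the overall interpretation". It also relies on the outcomes having been prespecified. With two thresholds in the document, the prespecification of this outcome is incomplete.

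**Working it through.** **Step 1: compare the statements.**

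| Place | Threshold | Time point | Baseline reference |
|---|---|---|---|
| Synopsis, Secondary Endpoints | 50% | 3 months | yes |
| Section 3.2, Depression item 2 | 50% | 3 months | yes |
| Section 10.5, Depression | 5% | none | none |
| Section 11.2 | no PHQ-8 response entry | – | – |

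Section 10.5 is the only place that names a specific test for this endpoint. The synopsis analysis text only lists candidate tests for the whole set.

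**Step 2: compare with the parallel endpoint.** The Chronic Pain trial also has a percentage-reduction responder endpoint. Section 3.2 gives "Proportion of participants achieving clinically significant pain reduction (30% reduction from baseline"; section 10.5 gives "secondary endpoint clinically significant pain reduction, defined as a 30% decrease"; section 11.2 gives a follow-up to baseline ratio of 0.7 or less, and 1 − 0.30 = 0.70. All three agree. Of these two responder endpoints, only the Depression one changes between definition and analysis.

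**Step 3: size of the difference.** The only input is the PHQ-8 range of 0 to 24 in section 11.2; the score is a sum of item responses, taken as whole numbers. For baseline b, the smallest qualifying fall is ceil(0.05 × b) under the 5% rule and ceil(0.50 × b) under the 50% rule.

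| Baseline b | 0.05 × b | Fall needed, 5% | 0.50 × b | Fall needed, 50% | Follow-up scores that count only under 5% |
|---|---|---|---|---|---|
| 1 | 0.05 | 1 | 0.5 | 1 | none |
| 2 | 0.10 | 1 | 1.0 | 1 | none |
| 10 | 0.50 | 1 | 5.0 | 5 | 6 to 9 (4 values) |
| 16 | 0.80 | 1 | 8.0 | 8 | 9 to 15 (7 values) |
| 20 | 1.00 | 1 | 10.0 | 10 | 11 to 19 (9 values) |
| 21 | 1.05 | 2 | 10.5 | 11 | 11 to 19 (9 values) |
| 24 | 1.20 | 2 | 12.0 | 12 | 13 to 22 (10 values) |

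The last column counts ceil(0.50 × b) − ceil(0.05 × b) values. Because 0.05 × 20 = 1 exactly, the 5% rule needs 1 point for every baseline from 1 to 20 and 2 points from 21 to 24. One point is the smallest change the scale can record. At b = 3 the 50% rule already needs 2 points against 1, so the rules agree only at baselines 1 and 2 and differ at every baseline from 3 to 24.

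**Step 4: does any planned number depend on it?** Section 10.1 sizes the Depression trial on the PROMIS depression T-score: standardized effect 0.28, two-sided alpha 0.049, power 90%, 271 per arm. Solving the two-sample t-test gives 270.4, which rounds up to 271, so the plan's figure reproduces. No PHQ-8 quantity enters the calculation.

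**The case against.** The strongest reply is that this is a slip nobody would act on. Section 3.2 is the endpoint section, the synopsis matches it word for word, and section 10.5 omits cut-offs and time points for remission too, so an analyst must consult sections 3.2 and 11.2 in any case. The synopsis analysis text covers all depression secondary endpoints, and within the synopsis this one is 50%. The separate Depression SAP may already say 50%. It is one of six Depression secondary endpoints.

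Much of that stands. A dropped zero is the likely explanation, and an analyst would probably notice. But for remission the missing detail is supplied by section 11.2 without conflict; for PHQ-8 response, section 10.5 states a figure that contradicts the definition, and section 11.2 supplies nothing. A SAP drafted from section 10.5 could inherit the error.

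The amendment log entry for the insertion also reads "and achieving 5% reduction in PHQ-8 scores". That records the same insertion and is not independent evidence that 5% was intended.

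A reader might infer more than the documents support:

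- That no other analysis text touches this endpoint. The synopsis does, though it assigns no specific test.
- That the trial's power or sample size is affected. Step 4 shows that it is not.
- That the looser rule favours the intervention, or yields a known false-response rate. The same rule would apply to both arms, and the documents give no PHQ-8 baseline or change distribution from which to derive responder rates.

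**Conclusion.** Wrong as written. The current section 10.5 text states a threshold for PHQ-8 response that contradicts the endpoint's definition in the synopsis and section 3.2, and omits the 3-month visit and the baseline reference. Applied literally, it is met by a 1-point fall from baselines 1 to 20 and a 2-point fall from 21 to 24, and it defines a different outcome at every baseline from 3 to 24.

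This rests only on the quoted text and the stated 0 to 24 range, with whole-number scores. The consequence is limited to one secondary endpoint reported with an unadjusted p-value. Whether the separate Depression SAP carries the right definition cannot be seen from these documents; if it does, the protocol text still needs correcting.

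**What to change.** In section 10.5 (Depression), replace the 5% wording with the definition already in section 3.2: "Achieve 50% reduction in PHQ-8 scores at 3 months, relative to baseline". Check that the separate Depression SAP and its programming specification use the same definition, before any unblinded analysis of this endpoint.

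Optionally, add a PHQ-8 response entry to section 11.2, in the form already used there for clinically significant pain reduction.

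The cost is one corrected line and, if wanted, one added definition. Data collection, sample size and the planned test do not change.

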## 10.6 Other Planned Analyses

### **Exploratory endpoints or comparisons of endpoints that will be considered:**

- Medication side effects
- Comparisons of measures of depression and/or pain
- Provider actions taken after CDS alerts

### **Sub-groups that will be considered:**

- All randomized participants
- Metabolizer phenotypes: UMs, RMs, NMs, IMs, and PMs.
- CYP2D6 or CYP2C19 activity scores
- Pediatric participants
- Adult participants
- “Per-protocol” - participants with both an actionable phenotype and concordance between the recommended medication/dosage and the prescribed medication and/or dosage
- Participants with an actionable phenotype, a discordant medication at baseline, and a concordant medication at the end of the study
- Stratified by medication, medication class and/or medications combinations
- Stratified by demographic characteristics (e.g. age, sex, gender and/or race)
- Stratified by type and/or design of CDS implemented
- Stratified by institution, enrolling site, and/or practice setting specialty (e.g. psychiatry, primary care, etc.)
- And other relative combinations of the above sub-groups

In addition to the primary research exploratory analyses, we will also analyze the uptake and utilization of the clinical decision support (CDS) tools that were created and its role in any medication changes made by providers. We will examine the impact of the CDS tools on various primary and secondary outcomes. We may also describe the development of the CDS tools, with a specific focus on the automated phenoconversion calculations implemented by some sites. As part of these analyses, we may collect and/or include the following data points: socio-demographics, health care characteristics (i.e. comorbidities), site ID, clinical group ID, CDS related data points (i.e. alert ID, CDS name, CDS alert type, date triggered, provider action), prescriber specialty, medication details (i.e. triggering medications, medication or dose changes, medication concordance/discordance), genotype and phenoconversion results.

We will also analyze reach, adoption, and implementation of the trial and PGx testing. We will examine enrollment and screening information, missing data rates, visit completion information. We will also analyze patient preferences for contact and survey administration, in addition to survey completion information

### **Specified analyses:**

#### All Trials

**Medication side effects.** The frequency and severity of medication side effects within each trial and trial arm will be summarized using standard descriptive statistics for discrete data (counts and percentages).

#### Acute Pain

**Trends in endpoints.** In addition to the primary and secondary endpoints described above, we will compare the time trends in the endpoints: pain scores, opioid usage, opioid misuse score, and mobility score at baseline, 1, 3, and 6 months among the CYP2D6 IM or PM subgroup, using a repeated-measures mixed effect model or generalized repeated-measures mixed effect model, as appropriate. Since participants are randomized to Intervention and Control groups and not to the CYP2D6 IM or PM subgroup within Intervention and Control groups, there could be important differences in baseline characteristics between the two groups. For these reasons, we will conduct covariate-adjusted repeated measures mixed models that will account for differences in baseline characteristics that differ between the Intervention – CYP2D6 IM or PM subgroup and the Control – CYP2D6 IM or PM subgroup. Potential baseline characteristics may include age, sex, income, education, insurance, surgical procedure type. We will select the appropriate covariance matrix (e.g. compound symmetry, autoregressive, unstructured, or other covariance structure) based on the data.

**Difference within the NM group.** In the control arm participants, we will compare pain scores in participants with a CYP2D6 activity score  $>0.75 - 1$  to participants with an activity scores  $>1-2$  using a two-sided two-sample t-test or Mann Whitney test, as appropriate, with a type 1 error of 0.05. Additionally, we will use linear regression to adjust for differences in baseline characteristics.

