## **2.2 Aims and Objectives of the Study**

Our rationale for examining a genotype-guided approach to acute and chronic pain management is based on the importance of *CYP2D6* for the bioactivation of tramadol, codeine, and hydrocodone and data from a pilot study supporting improved pain control in IM/PMs in the genotype-guided arm who are taking these drugs at baseline. Similarly, the rationale for examining a genotype-guided approach to depression medication therapy is based on the demonstrated role of *CYP2D6* in the bio inactivation and *CYP2C19* oxidation of select, commonly used SSRIs. Secondly, data from industry sponsored trials support the hypothesis of improved symptom control in a genotype-guided arm.

Acute Pain: Determine if a genotype-guided approach to acute post-surgical pain therapy leads to improved pain control compared to usual care, as defined by a decrease in the SIA score. Secondarily, we will evaluate whether this approach leads to reduced use of DEA Schedule II opioids and reduced pain intensity.

Chronic Pain: Determine if a genotype-guided approach to pain therapy in participants with at least 3 months of chronic pain leads to improved pain control compared to usual care.

Depression: Determine if genotype-guided dosing or selection of antidepressants among participants with at least 3 months of depressive symptoms who require new or revised antidepressant therapy leads to improved control of depression, compared to usual care.

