**Table 1. Genes to be tested and drugs with CPIC recommendations**

Genes	Drugs
CYP2C19	citalopram, escitalopram, sertraline
CYP2D6	codeine, oxycodone, tramadol, hydrocodone, fluvoxamine, paroxetine

*CYP2D6* phenotypes will be inferred based on the activity scoring system as shown in **Table 2 and Table 3**. The activity score value of each allele (**Table 2**) is added together to determine the total activity score for the diplotype. The activity scores are converted to phenotypes per **Table 3**. The IM phenotype will be defined as an activity score of >0 to 0.75, not >0.75 to 1.0. As there is debate about

how to define the IM phenotype, we will have an *a priori* analysis plan to determine whether participants in the usual care arm with an activity score of >0.75 to 1 (who we will define as NM) have worse pain control or depressive symptoms than NMs with an activity score > 1 to 2. If an allele is duplicated, and it is unknown which allele is duplicated, then the AS may be a ranged number, resulting in a ranged phenotype. If the ranged phenotype is NM-UM, the individual will be treated clinically as is if they were a UM.

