## 14. APPENDICES

### 14.1 APPENDIX A. SIA SCORE BACKGROUND AND RATIONALE

For the primary endpoint, we propose to use a composite score that captures both opioid consumption (MED) and pain intensity. This is based on preliminary data from a University of Florida (UF) pilot study in which CYP2D6 genotype-guided opioid prescribing after arthroplasty surgery was compared to a usual care approach (ClinicalTrials.gov Identifier: NCT03534063). While not powered to detect differences in clinical endpoints, preliminary results from 174 patients showed similar pain intensity at 2-week post-surgery between genotype-guided and usual care groups, but significantly lower MMEs in the genotype-guided group. The combination of lower opioid consumption with similar pain intensity indicates better pain control in the genotype-guided arm. However, assessing opioid consumption and pain intensity as two separate variables fails to characterize the inter-individual differences in opioid use as pain intensity changes over time, which is why we believe a composite endpoint that integrates the two is justifiable.

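### The acute pain check of the IM cut-off compares pain scores only, so it cannot see a disadvantage that patients offset by taking more opioid

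*Combined protocol and SAP*

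**What the plan says.** Section 7.1 (text under Table 1) acknowledges that the IM definition is debated and undertakes to examine whether usual-care participants at >0.75 to 1 "have worse pain control or depressive symptoms than NMs with an activity score" of >1 to 2. The note to Table 3 says that the trial's IM definition differs from current CPIC guidelines. The same cut-off (activity score up to 0.75) defines the acute pain analysis population in section 10.3.

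Section 10.6, Acute Pain, 'Difference within the NM group', implements the check: "In the control arm participants, we will compare pain scores in participants with a CYP2D6 activity score" of >0.75 to 1 and those at >1 to 2, "using a two-sided two-sample t-test or Mann Whitney test, as appropriate, with a type 1 error of 0.05", with a linear regression to adjust for baseline differences. It names no pain scale and no time point. The paragraph before it lists pain scores and opioid usage as separate endpoints, so the first does not include the second.

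Section 2.2 states the acute pain aim as whether genotype-guided therapy "leads to improved pain control compared to usual care, as defined by a decrease in the SIA score". Appendix A supports the composite with a pilot whose "preliminary results from 174 patients showed similar pain intensity at 2-week post-surgery between genotype-guided and usual care groups, but significantly lower MMEs" in the guided arm, and argues that "assessing opioid consumption and pain intensity as two separate variables fails to characterize the inter-individual differences in opioid use" as pain changes over time.

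**The concern.** The check asks whether patients just above the cut-off behave like normal metabolizers. After surgery, a patient who gets less relief per tablet can report more pain, take more tablets, or do some of each. A comparison of pain scores sees only the first response. Appendix A makes this argument for the primary endpoint, but the check of the cut-off does not carry it through.

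The other two trials handle the same check differently. Chronic pain compares pain scores and pain control; depression compares depression scores and depression control. In both, the second item is the construct behind the primary endpoint. Only acute pain leaves that construct out, which looks like a drafting gap.

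What is at stake is the reading of a null result. If score-1 patients reach the same pain level with more opioid, the planned comparison would show no difference, and a report could take that as reassurance about the cut-off.

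**Working it through.** **Reproducing the plan's figure.** Section 10.1 uses effect size 0.375, two-sided alpha 0.049 and 90% power. The exact two-sample t-test solves to 151.2, so 152 per arm, as stated. Then 152 / 0.18 = 844.4, so 845 completers per arm, as in Table 9. The plan states no sample size or power for the NM check.

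**Size of the NM check.**
- Control-arm completers: 845 (Table 9). IM/PM: 18% (section 10.1). UM: 2%, the upper end of the range in section 2.1.
- Control-arm NMs: 845 × (1 − 0.18 − 0.02) = 676.
- Share of NMs at >0.75 to 1: not in the documents. Assumed 30% (203 v 473), range 15% to 50%.

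**Power if pain differs.** The difference detectable with 80% power at two-sided 0.05 is (1.960 + 0.842) × √(1/n₁ + 1/n₂) in SD units. At 203 v 473 this is 2.802 × 0.0839 = 0.235 SD. Over 15% to 50% it runs from 0.30 to 0.22 SD, and power for 0.3 SD runs from 79% to 97%. With the Synopsis figure of 1,730 randomized: 1,730 × 0.90 × 0.93 / 2 = 724 completers, about 579 NMs, and 0.33 to 0.23 SD. The check is not underpowered for pain.

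**Where the effect appears.** By section 11.2 the SIA score is the sum of two percentile ranks, each scaled to −100 to 100. If the ranks are uniform, each component has SD 200/√12 = 57.7. The pilot SIA SD of 93.5 (section 10.1) then implies a pain–opioid correlation of 93.5² / (2 × 57.7²) − 1 = 0.31. Component shifts of d_pain and d_opioid SD give an SIA effect of (d_pain + d_opioid) × 57.7 / 93.5. Power at 203 v 473, two-sided t-test at 0.05:

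| Shift (SD): pain, opioid | SIA effect | Pain scores | Opioid usage | SIA |
|---|---|---|---|---|
| 0, 0.3 | 0.185 | 5% | 95% | 60% |
| 0.3, 0 | 0.185 | 95% | 5% | 60% |
| 0.2, 0.2 | 0.247 | 66% | 66% | 84% |

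The 5% entries are simply the error rate when that component has no shift. The shifts are assumptions, since the documents report no pain or opioid data by activity score within usual care.

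**Scaling to the pilot.** As a further assumption, carry half the pilot SIA difference (38.55 / 2 = 19.3; 19.3 / 93.5 = 0.206 SD) over to this contrast. SIA has 69% power. Pain alone has 5%, 7%, 17% and 51% when pain carries 0%, 10%, 25% and 50% of the difference.

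**The case against.** A reader might infer that a reassuring null is close to built in, because the pilot found similar pain with different opioid use. The documents do not support that.
- The pilot contrast is between randomized arms, where the intervention changes prescribing. It is not between activity-score groups within usual care.
- Appendix A says that the pilot was not powered for clinical endpoints. With 174 patients split evenly (assumed), the 95% half-width for pain is 1.96 × √(2/87) = 0.30 SD, so similar pain is weak evidence of equal pain.
- Appendix A also describes the pilot's SIA result as less pain together with fewer opioids (p = 0.07).
- A 5% rejection rate for pain follows only from setting the pain difference to zero.

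These points stand. So does the objection to replacing pain by SIA: if only pain differs, SIA loses power (60% against 95% above), so neither outcome dominates.

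The textual mismatch is also less than complete. Section 11.2 gives a general definition of pain control as change in pain intensity, and Appendix A in places speaks of opioid use and pain control as two things. Section 2.2 nevertheless ties acute pain control to the SIA score, and the check in section 10.6 does not specify change from baseline either.

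Nor does the plan say that a null result would support the cut-off. There is no decision rule, the IM definition is fixed whatever the result, and section 10.9 promises cautious interpretation. Section 10.6 lists activity scores among possible sub-groups and comparisons of pain measures among exploratory endpoints, and sections 10.2 and 10.6 leave detail to a separate SAP. None of this commits to SIA or opioid usage for this check.

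**Conclusion.** The point holds in a limited form. The acute pain check omits the construct by which section 2.2 defines acute pain control, and differs in this from its two parallel checks. It has reasonable power if pain itself differs by about 0.3 SD (79% to 97% with 15% to 50% of about 676 NMs at >0.75 to 1). It cannot detect a disadvantage wholly offset by opioid intake, and has little power when most of the effect appears there. A non-significant pain comparison alone should therefore not be read as support for the cut-off.

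How likely such offsetting is between these two groups cannot be judged from the documents. The sizes rest on the assumed NM split, the assumed shifts and uniform component ranks. The analysis is exploratory: the primary test, the analysis population and the prescribing recommendations do not depend on it. This is a cheap improvement, not a defect in the trial's main inference.

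**What to change.** In section 10.6, Acute Pain, 'Difference within the NM group', compare three 10-day outcomes between the two activity-score ranges: pain intensity, opioid usage and the SIA score. Add the last two; do not drop pain. Name the pain scale, because section 7.3 gives acute pain both a 0–10 rating and a three-item scale, and state the population in which the SIA ranks are formed. Report each difference with a confidence interval, and add a sentence that a non-significant pain comparison alone will not be taken as support for the cut-off.

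The cost is a few lines of text and two more exploratory comparisons. All three outcomes are already collected or derived for the primary and secondary endpoints. SIA is less powerful than pain when only pain differs; keeping the pain comparison covers that case.
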